Section 6.2.1	Intraocular Inflammation and Immunogenicity Related to RST-001  During the study, evidence of immune response to RST-001 will be monitored by systemic measurement of humoral and cellular immunity as follows:  [REDACTED]  These tests will be performed at several timepoints during the study: baseline (pre-dose)  [REDACTED]  Treatment of intraocular inflammation and immunogenicity In the event that immunogenicity is suspected by the investigator, topical, local, intraocular or systemic corticosteroid, corticosteroid-sparing and immunomodulatory therapy may be initiated, usually in an escalating fashion, in accordance with the investigator's practice, to control the inflammation. The patient will continue in the study and all additional assessments and visits will be documented in the source documents.	Incorporation of protocol amendments made by RetroSense in response to FDA comments in 2015
Section 6.2.4	Female patients of childbearing potential will require a pregnancy test at study exit Month 24 or early termination visit.	Month 24 is no longer study exit

Section	Revision	Rationale
Section 7.3	
2. Advise on dose-escalation, Phase 2a sample size/study population, study suspension or termination, as appropriate.
 
3. Provide review and advice on protocol amendments and changes to the clinical protocol, as appropriate.
 
4. Provide advice on any other matters as deemed necessary for the safe conduct of the study.
 
5. Provide assessment as to whether treatment benefits have been observed in Phase 1 of the study.
	Reflects the responsibility of establishing the cohort size and eligibility for Phase 2a
Section 7.4	
Enrollment will be suspended pending a complete safety review by the sponsor of all patients including causality to determine the appropriateness of continuing dosing in the occurrence of the following events:
 
 
1. Any Grade 3 or greater AE related to RST-001 (according to Common Terminology Criteria for Adverse Events v4.03)
 
2. Occurrence of an intraocular infection related to contaminated RST-001 that required treatment would serve as a stopping rule. Any evidence that the delivered product carries an infectious agent
 
3. A safety issue has been identified that compromises the benefit or increases the risk balance
 
 
Dose-limiting toxicity (DLT) is defined as any adverse event of Grade 3 or higher that is possibly, probably or definitely expected to be related to the study treatment. DosingDose escalation will stop if a DLT is observed, including:
	Incorporation of protocol amendments made by RetroSense in response to FDA comments in 2015
Section 8	The entire Adverse Events section has been removed and replaced with language that aligns with Allergan standards	Change to Allergan standards for consistency in AE reporting Edited for clarity.
Section 11.2.1.1	Change in visual acuity in the treated study eye from Baseline (defined as last observed value prior to dosing ) to [REDACTED].	
Section 11.3.1	No The sample size for this study was chosen empirically ; no formal sample size computations to meet power requirements were made. The sample size for this study was chosen empirically, as reasonable to answer the primary safety objective . The sample size of approximately 3 patients per single for each dose cohort and a total of 15 patients group in Phase 1 are typical for Phase I/II dose escalation studies of this type, and are expected to provide a sufficient number of observations to meet the objectives of the study, an additional up to approximately 12 patients will be enrolled in Phase 2a for further safety and efficacy evaluation .	Reflects a potentially larger sample size

Section	Revision	Rationale
Section 11.3.4	Efficacy will be measured by evaluation of visual acuity, full field sensitivity, ambulation, quality of life and electrophysiological measures (visual evoked potentials, electroretinography ). Visual acuity data will be presented as the number of letters correctly identified at each time point and the calculated logMAR and Snellen equivalent values., or as count fingers, hand motion, and light perception . The Quality-of-life questionnairesquestionnaire will be scored using the NEI VFQ-25 scoring algorithm.	Edited for clarity
Section 11.3.5	Immune responses will be measured quantitatively (qualitatively along with [REDACTED])	Edited for clarity
Section 11.3.6	
Enrollment will begin with Group A in Phase 1 and will proceed to subsequent groups after satisfactory review of safety data by a DSMC. After completion of this first phase of the study, patients will be treated in Phase IIa of the study.
 
Before each DSMC review, the investigators and sponsor will prepare a summary of all available data. For DSMC reviews related to enrollment in subsequent groups, this summary will include data through a minimum of Month 1 Visit for all available patients.
 
There will be three database locks. The primary analysis will occur when all patients have completed the Month 6 visit, or exited earlier. The second analysis will occur when all patients have completed the Month 24 visit or exited early from the study. The final analysis will occur when all patients have completed the long-term follow-up or have been lost to follow-up. The details of all analyses will be provided in the analysis plan which will be finalized before database lock for the primary analysis at Month 6.
	Edited for clarity
Section 17	
Authorship will be determined by mutual agreement and in line with International Committee of Medical Journal Editors authorship requirements
	Removed to align with Allergan's publication policy standards.

## 20.5 Protocol Amendment Summary Amendment 3

Title: Phase I/IIa, Open-Label, Dose-Escalation Study of Safety and Tolerability of Intravitreal RST-001 in Patients with Retinitis Pigmentosa (RP)

### Protocol RST-001-CP-0001 Amendment 3: (August 2022)

#### Amendment Summary

This summary includes changes made to Protocol RST-001-CP-0001 Amendment 2 (approved October 19, 2017). The main reason for this amendment was to reduce the long-term follow-up period from 13 years to 3 years in this protocol.

Following is a summary of content-oriented changes that were made to each section of the protocol, and a brief rationale for these changes. Minor editorial and document formatting revisions have not been summarized. Deleted text is indicated by strikethrough and added text is underlined, as appropriate. This summary provides a high-level list of changes to the document.

Section	Revision	Rationale
Title Page	
[REDACTED], MD
 
Tel (office): [REDACTED]
 
Tel (mobile): [REDACTED]
 
Email: [REDACTED]
 
[REDACTED] -MD
 
Tel (office): [REDACTED]
 
Tel (mobile): [REDACTED]
 
[contact]
 
Email: [REDACTED]
 
[REDACTED]
	Change from Medical Safety Physician to Medical Monitor
Title Page	
[REDACTED]
 
[REDACTED]
 
Allergan Global Drug Development
	Remove Allergan signatory to align with current SOPs
Section 2, Protocol Synopsis		Reduce long-term follow-up
Study Design	Duration: 2 years (with an additional 43 years of long-term follow-up)	
Visit Schedule	
Long-term follow-up: After completion of the Month 24 visit, each patient will participate in a long-term follow-up study for an additional 43 years to monitor the long-term safety of RST-001. This includes a yearly visit for <del>5</del> 3 years (Months 36, 48, and 60, 72, and 84). After <del>5</del> years, telephone interviews will be conducted over an 8 year period (Months 96, 108, 120, 132, 144, 156, 168, and 180) for a total 13 years of long term follow up.
	
Section 3.15.1.1, Enrollment Phase 1	After completion of the 2-year core study visits, each patient will be enrolled in a long-term follow-up for an additional 43 years to monitor the long-term safety of RST 001.	Reduce long-term follow-up

Section	Revision	Rationale
Section 3.15.1.2, Enrollment Phase 2a	After completion of the 2-year core study visits, each patient will be enrolled in a long-term follow-up for an additional 43 years to monitor the long-term safety of RST-001.	Reduce long-term follow-up
Section 5, Study Assessments and Intravitreal Injection	
 
Long-term follow-up: After completion of the Month 24 visit, each patient will participate in a long-term follow-up study for a total of an additional 13 years. These visits include yearly office visits for 5 years (Months 36, 48, and 60, 72, and 84) and yearly teleconference interviews for 8 years (Months 96, 108, 120, 132, 144, 156, 168, and 180).
 
 
Table 3: Removed columns for Month 72 and 84 visits and all teleconference interviews
	Reduce long-term follow-up
Section 5.1.14, Long-term Follow-up Visits	
Patients completing the Month 24 visit will participate in long-term follow-up visits. Patients will be asked to report any AEs that occur during this 43-year follow-up period. At Months 36, 48, and 60, 72, and 84, patients will undergo the following study assessments conducted at yearly clinic visits:
 
 
Concomitant medications and procedures
 
AE review
 
Visual acuity
 
Complete ophthalmic examination
 
 
The procedures for these assessments will be the same as they were for the core study assessments.
 
<del>At Months 96, 108, 120, 132, 144, 156, 168, and 180 patients will not be required to attend for study assessments. Instead, concomitant medications and procedures and AE review will be conducted via annual teleconference interviews.</del>
	Reduce long-term follow-up
Section 11.3.6, Interim Analysis	
No interim analysis is planned. There will be <del>three</del> two database locks. The primary analysis will occur when all patients have completed the Month 6 24 visit, or exited <del>earlier</del> early from the study. The <del>second</del> analysis will occur when all patients have completed the Month 24 visit or exited early from the study. The final analysis will occur when all patients have completed the long-term follow-up or have been lost to follow-up. The details of all analyses will be provided in the analysis plan which will be finalized before database lock. <del>for the primary analysis at Month 6.</del>
	Reduce the database locks from three to two and revise the timing for the primary analysis

## 20.6 Protocol Amendment Summary Amendment 4

Title: Phase I/IIa, Open-Label, Dose-Escalation Study of Safety and Tolerability of Intravitreal RST-001 in Patients with Advanced Retinitis Pigmentosa (RP)

### Protocol RST-001-CP-0001 Amendment 4: (November 2022)

#### Amendment Summary

This summary includes changes made to Protocol RST-001-CP-0001 Amendment 4 (approved November 22, 2022). The main reason for this amendment was to include content related to virtual visits in case of COVID-19 and COVID-19 infection reporting, update contact information for AE reporting, and clarify timing for the final analysis.

Following is a summary of content-oriented changes that were made to each section of the protocol, and a brief rationale for these changes. Minor editorial and document formatting revisions have not been summarized. Deleted text is indicated by strikethrough and added text is underlined, as appropriate. This summary provides a high-level list of changes to the document.

Section	Revision	Rationale
Section 5, Study Assessments and Intravitreal Injection	
Study visits may be impacted due to the COVID-19 pandemic. This may include changes such as telephone or virtual visits, visits at alternative locations, or changes in the visit frequency and timing of study procedures, among others. Additional details are provided in the subsequent section.
 
Every effort is to be made to ensure the safety of subjects and site staff, while maintaining the integrity of the study. If visits cannot be conducted onsite due to travel restrictions or other pandemic-related reasons, follow the updates below on how to proceed.
 
During the COVID-19 pandemic, if it is not possible for all study procedures to be performed as specified due to travel restrictions or other reasons, the following modifications are allowed with agreement from the sponsor:
 
 
• If permitted by local regulations, the IRB/IEC, and the subject, postbaseline visits may be conducted virtually.
 
• Study Visits and/or activities are to be performed as scheduled whenever possible.
 
	Provide content related to virtual visits in case of COVID-19
Section 5.1.1, Informed Consent and Patient Privacy	
Due to the COVID-19 pandemic, it is possible that protocol modifications may become necessary. If this situation arises, in addition to the study informed consent, additional verbal consent may be obtained prior to these adaptations or substantial changes in study conduct in accordance with local regulations.
	Provide content related to virtual visits in case of COVID-19

Section	Revision	Rationale
Section 5.2.3, Concomitant Medications and Procedures	
Given the ongoing COVID-19 pandemic, selected non-live vaccines (e.g., mRNA, non-replicating viral vector, protein subunit) to prevent Severe Acute Respiratory Syndrome Coronavirus 2 (SARS-CoV-2) infection may be administered during screening or the treatment period, as long as components of the vaccine are not contraindicated.
 
The decision to receive a locally available vaccine is to be based on local guidance and an individual discussion between the treating physician and the subject.
 
The potential impact of RST-001 on SARS-CoV-2 vaccination is unknown.
	Provide content related to the SARS-CoV-2 vaccination
Section 5.2.4, Adverse Event Review	COVID-19 infections should be reported as AEs.	Provide content for reporting COVID-19 infections
Section 8.2, Procedures for Reporting Adverse Events	
SARS-CoV-2 infections are to be captured as AEs. If the event meets the criteria for a serious adverse event, then follow the serious adverse event reporting directions.
 
Reactions known to be associated with the SARS-CoV-2 vaccine are to be reported as AEs. If the event meets the criteria for a serious adverse event, then follow the serious adverse event reporting directions.
	Provide content for reporting COVID-19 infections
Section 8.3, Procedures for Reporting a Serious Adverse Event	
Pregnancy
 
While not an AE, pregnancy in a study participant must be reported to Allergan within 24 hours after the site becomes aware of the pregnancy. If a pregnancy occurs in a study participant or in the partner of a study participant, information regarding the pregnancy and the outcome will be collected.
 
The pregnancy outcome of an elective or spontaneous abortion, stillbirth or congenital anomaly is considered a serious adverse event and must be reported to Allergan within 24 hours after the site becomes aware of the event.
	Provide content for reporting pregnancies.
Section 10.1, Monitoring	During the COVID-19 pandemic, remote data review/verification may be employed if allowed by the local regulatory authority, IRB/IEC, and the study site.	Provide content for remote data review
Section 11.3.6, Interim Analysis	No interim analysis is planned. There will be <del>two</del> <ins>one</ins> database locks <del>for the final analysis. The primary analysis will occur when all patients have completed the Month 24 visit or exited early from the study.</del> The final analysis will occur when all patients have completed the <del>Month 60 visit or exited early from the study</del> <ins>long term follow up or have been lost to follow up</ins> . The details of all analyses will be provided in the analysis plan, which will be finalized before database lock.	Reduce the database lock from two to one and clarify the timing for the primary analysis

3.0 LIST OF ABBREVIATIONS

AE	adverse event
eCRF	electronic Case Report Form
ECG	electrocardiogram, electrocardiographic
ERG	Electroretinography
IOP	Intraocular Pressure
MedDRA	Medical Dictionary for Regulatory Activities
PCS	potentially clinically significant
PT	Preferred Term
SAE	serious adverse event
SAP	statistical analysis plan
SD-OCT	Spectral Domain Optical Coherence Tomography
SI	Le Système International d'Unités (International System of Units)
SOC	System Organ Class
TEAE	treatment-emergent adverse event
VEP	Visual Evoked Potentials

4.0 INTRODUCTION

This statistical analysis plan (SAP) provides a more technical and detailed elaboration of the statistical analyses of the safety and efficacy data as specified in the current protocol of Study RST-001-CP-0001 (amendment #2 dated 19 Oct 2017). Specifications of tables, figures, and data listings are contained in a separate document.

Study RST-001-CP-0001 is a Phase 1/2a, open-label, dose-escalation, non-randomized study of safety and tolerability of Intravitreal RST-001 in patients at least 18 years of age who have been diagnosed with advanced RP using criteria including clinical diagnosis, documented retinal electrophysiological evidence of rod-cone photoreceptor degeneration and baseline evidence of <10 microvolts (μ V) maximal b-wave electroretinography (ERG) response.

[figure not shown]
The length of this study participation will be 2 years with an additional 13 years of long-term follow-up.

Patients meeting the inclusion/exclusion criteria will receive a single 100 μ L intravitreal injection of RST-001 in the study eye. In Phase 1, three doses of RST-001 (low, mid and high), each group comprising of approximately but no less than three patients) will be evaluated by sequential dose escalation. In Phase 2a, up to 12 patients may be enrolled and receive RST-001 at the maximum tolerated dose. Patients who withdraw from the study prior to receiving the study treatment may be replaced.

The three doses of RST-001 are as follows:

	LOW Dose	MID Dose	HIGH Dose
RST-001	[REDACTED] vg/eye	[REDACTED] vg/eye	[REDACTED] vg/eye

The study design is shown graphically in Figure 4-1. The dose-escalation cohorts are illustrated in Table 4-1 below. The schedule of evaluations for Study RST-001-CP-0001 is presented in 2 and Table 4-3.

Figure 4–1. Overview of the Treatment Schedule**Table 4–2. Dose Escalation**

Phase	Group	Number of patients ^a	Intravitreal Injection	
			Vector concentration	Volume (µL)
1	A	3	LOW	100
	B	3	MID	100
	C	3	HIGH	100
2a		6-12 ^b	Choice of dose ^c from groups A, B, or C	100

^a Up to approximately 21 patients will be enrolled in this study.^b Number of patients is dependent upon whether or not the DSMC determines that, in their opinion, a treatment benefit for visual acuity/function has been observed in Phase 1.^c The maximum tolerated dose.

Table 4–3. Study Visit Schedule: Core Study Visits

	Screening ^b	Baseline ^b	Day			Month					
			0	1	7 ± 1	1 ± 7	3 ± 7	6 ± 7	9 ± 7	12 ± 30	18 ± 30
Visit Windows (Days) ^a	-45 to -8	-7 to -1	0	1	7 ± 1	1 ± 7	3 ± 7	6 ± 7	9 ± 7	12 ± 30	18 ± 30
Informed Consent/Authorization	X										
Ophthalmic and Medical History	X	X	X								
Concomitant medications and procedures	X	X	X	X	X	X	X	X	X	X	X
Adverse Events review	X	X	X	X	X	X	X	X	X	X	X
Physical Examination	X										
Pregnancy Test	X	X									
Blood Sample ^d	X	X									
Electrocardiogram (ECG)	X										
Chest X-ray	X										
Visual acuity	X	X									
Full Field Sensitivity Testing (FFST)	X	X									
Object detection and discrimination	X	X									
Pupillometry (at selected sites)		X									
Ambulation		X									
Complete Ophthalmic Examination	X	X									
Intraocular Pressure (IOP)	X	X									
Spectral Domain Optical Coherence Tomography (SD-OCT)	X	X									
Color Fundus Photography and Autofluorescence		X									
Electroretinography (ERG)	X										
Visual Evoked Potentials (VEP)		X									
Quality-of-life questionnaire		X									
Study drug administration ^f											

- a Assessment administration may extend over more than one day.
- b If convenient, the Screening and Baseline visits may be combined.
- c Month 24 or early termination visit.
- d Blood samples will include hematology, chemistry and RST-001 immunogenicity testing: see Protocol [Appendix 2](#) for details.
- e IOP measurements will be performed pre- and post-injection in the study eye only. After the intravitreal injection, the patient will remain in the supine position and (IOP) intraocular pressure will be monitored for at least 30 min. In the event that the IOP is 30 mmHg or above, this will be managed according to protocol (Section 5.3.2).
- f Topical corticosteroid treatment may be given to the injected eye according to the investigator's standard of care.

Table 4-4. Study Visit Schedule: Long-term Follow-up Visits

Visit Windows (Month \pm Days)	Months											
	Clinic Visits						Teleconference Interviews					
	36 \pm 30	48 \pm 30	60 \pm 30	72 \pm 30	84 \pm 30	96 \pm 30	108 \pm 30	120 \pm 30	132 \pm 30	144 \pm 30	156 \pm 30	168 \pm 30
Concomitant medications and procedures	X	X	X	X	X	X	X	X	X	X	X	X
Adverse Events review	X	X	X	X	X	X	X	X	X	X	X	X
Visual Acuity	X	X	X	X	X							
Complete Ophthalmic Examination	X	X	X	X	X							

5.0 OBJECTIVES AND ENDPOINTS

The primary objective of this study is to evaluate the safety of a single intravitreal injection of RST-001.

The secondary objectives of this study are

1. To establish the maximum tolerated dose of RST-001.
2. To evaluate the preliminary efficacy of RST-001 in patients with advanced RP.

The therapy will be considered safe in the absence of any grade 3 or greater AE considered related to RST-001.

Other safety measurements for the primary objective will be assessed by visual function measures at [REDACTED] including:

- Change in visual acuity (VA) from baseline (defined as last observed value prior to dosing) in the study eye
- Change in full field sensitivity from baseline in the study eye
- Change in ambulation scores from baseline
- IOP measurements from baseline in the study eye
- Change in anatomical parameters from baseline as measured in the study eye:
 - Fundus photography
 - Spectral domain-OCT (SD-OCT)

The effect of intravitreal injection of RST-001 in improving visual function as measured by a series of psychophysical, electrophysiological and anatomical measures.

The secondary endpoints include the following efficacy measures of change in visual function:

- Change in VA in the study eye from baseline to [REDACTED]
- Change in full field sensitivity in the study eye from baseline to [REDACTED]
[REDACTED]
- Change in ambulation scores from baseline to [REDACTED]

- Change in object detection and discrimination scores from baseline to [REDACTED]
[REDACTED]
- Change in visual evoked potentials (VEP) and electroretinography (ERG) scores from baseline to [REDACTED]
- Change in composite score of NEI VFQ-25 scores from baseline to [REDACTED]
[REDACTED]

The secondary endpoints also include the following measures of anatomical endpoints relating to retinal integrity and survival:

- Qualitative assessment of the change in retinal appearance (fundus photography) from baseline to [REDACTED]
- Qualitative assessment of the change in retinal cross-sectional appearance (SD-OTC) from baseline to [REDACTED]

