Justification for dose	
The doses and injection volume of RST-001 have been calculated by allometric scaling from pre-clinical animal studies. Vitreous humor volume was the scaling factor across species. Therefore, the scaling factor of the vitreous volume from mice and dogs to humans is 1:100 and 1:2, respectively. Two nonclinical toxicology studies were conducted in dogs and mice. The safe intravitreal doses in the dog ranged from [REDACTED] vg/eye. In mice, the safe intravitreal doses ranged from [REDACTED] vg/eye. Additionally, two nonclinical pharmacology studies demonstrated efficacy and safety in mice at a dose range of [REDACTED] to [REDACTED] vg/eye in a dose range comparable to the toxicology study. Based on these studies, the expected safe dose range of RST-001 in humans is between [REDACTED] and [REDACTED] vg/eye. In summary, the dose range in this FIH study [REDACTED] is based on the more conservative exposure in the dog, inclusion of potentially efficacious doses, the ability of the manufacturer to concentrate investigational product, and a safe injection volume of 100 <math>\mu</math>L per eye in humans.

Surgical procedure	
A single intravitreal injection of RST-001 in the study eye of patients with advanced RP.

Clinical Study progress	Patients will be enrolled sequentially. The decision to dose escalate will be determined with the DSMC upon review of adverse events (AE), clinical evaluations (ocular and systemic) and laboratory results.
Monitoring of safety and tolerability	Safety monitoring will include a combination of AE reporting, clinical evaluations (ocular and systemic), and laboratory results. Ocular and systemic safety monitoring will include monitoring for signs of an immune response.
Enrollment Stopping rules	Any Grade 3 (Common Terminology Criteria [CTC] for AEs v4.03) or greater AE considered related to the study treatment.
Primary endpoints: Assessment of safety	The primary endpoint is safety at 6 months from start of study treatment. The therapy will be considered safe in the absence of any grade 3 or greater AE considered related to RST-001.
Secondary endpoints	The effect of intravitreal injection of RST-001 in improving visual function as measured by a series of psychophysical, electrophysiological and anatomical measures.

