### **3.15.1.2 Enrollment Phase 2a**

If the DSMC considers the safety and tolerability satisfactory and the enrollment stopping rules have not been met after a minimum assessment of one month (to include Month 1 Visit) from treatment of the final patient in Groups A, B, or C, then the sponsor may elect to start enrollment in the second cohort of patients. In Phase 2a, up to approximately 12 patients may be enrolled and receive RST-001 at the maximum tolerated dose.

- If the DSMC considers the data from Phase 1, in their opinion, to be indicative of a treatment benefit for visual acuity/function, then approximately 6 patients will be enrolled in Phase 2a and follow the same eligibility criteria as Phase 1.
- If the DSMC considers the data from Phase 1, in their opinion, to **not** be indicative of a treatment benefit, then approximately 12 patients will be enrolled in Phase 2a.
  - 6 patients must have VA of no-better-than hand motion in the study eye.
  - 6 patients must have VA in the study eye to range from no-worse-than count fingers to 20/200 vision.

A schematic providing an overview of the treatment schedule is illustrated in [Figure 1](#), and the dose-escalation cohorts are illustrated in [Table 1](#) below.

**Figure 1** Overview of the Treatment Schedule**Table 1** Dose Escalation

Phase	Group	Number of patients a	Intravitreal Injection	
			Vector concentration	Volume (µL)
1	A	3	LOW	100
	B	3	MID	100
	C	3	HIGH	100
2a		6-12 b	Choice of dose c from groups A, B, or C	100

a Up to approximately 21 patients will be enrolled in this study.b Number of patients is dependent upon whether or not the DSMC determines that, in their opinion, a treatment benefit for visual acuity/function has been observed in Phase 1.c The maximum tolerated dose.

After completion of the 2-year core study visits, each patient will be enrolled in a long-term follow-up for an additional 3 years to monitor the long-term safety of RST-001.

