### **11.3.1 Power and Sample Size Considerations**

The sample size for this study was chosen empirically; no formal sample size computations to meet power requirements were made. The sample size of approximately 3 patients for each dose group in Phase 1 are typical for dose escalation studies, an additional up to approximately 12 patients will be enrolled in Phase 2a for further safety and efficacy evaluation.

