10.0 EFFICACY ANALYSES

All analyses will be based on the observed data. *Baseline* for efficacy is defined as the last non-missing efficacy assessment before the first dose of study treatment. All confidence intervals will be 2-sided 95% confidence intervals, unless stated otherwise.

The efficacy parameter will be the change from baseline VA, full field sensitivity, ambulation, object detection discrimination, VEP, ERG, QoL (composite score of NEI VFQ-25 scores) for the study eye at the scheduled Post-treatment visits and will be summarized by visit and by treatment group separately for each phase.

The NEI-VFQ-25 consists of 25 vision-targeted questions that represent 11 vision-related quality of life subscales and one additional general health item. The 11 subscales are general vision (item 2), difficulty with near vision activities (items 5, 6, 7), difficulty with distance vision activities (items 8, 9, 14), limitations in social functioning due to vision (items 11, 13), role limitations due to vision (items 17, 18), dependency on others due to vision (items 20, 23, 24), mental health symptoms due to vision (items 3, 21, 22, 25), driving difficulties (items 15c, 16, 16a), limitations with peripheral vision (item 10), limitation with color vision (item 12), and ocular pain (items 4, 19). The general health item is item 1.

Responses to individual questions are recoded to scores using the following scoring system, with a higher score representing better functionality. For example, for question 1, a score of 100 is applied for a response of “1.” The summary score for each subscale is determined by taking the average across multiple items within each corresponding subscale. For subscales calculated based on multiple questions, at least one non-missing response is required (i.e., at least one question is answered). The overall composite score is then calculated by averaging over all 11 vision-targeted subscale scores, excluding the general health score. Items or subscales that are left blank are excluded from the calculation of average scores; e.g., if any of the 11 subscale scores is missing, the overall composite score will be calculated based on the mean of the non-missing subscales.

Table 10-1 VFQ-25 Coded Values for Each Item

Items	Response Level	Coded value
1, 3, 4, 15c ^a	1	100 (best)
	2	75
	3	50
	4	25
	5 ^b	0 (worst)
2	1	100 (best)
	2	80
	3	60
	4	40
	5	20
	6	0 (worst)
5-14, 16, 16a	1	100 (best)
	2	75
	3	50
	4	25
	5	0 (worst)
	6	Missing

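### The plan calls the therapy safe if no related Grade 3+ event occurs, with no precision statement, at sizes that leave rates of 16% to 34% not excluded

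*SAP*

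**What the plan says.** SAP 5.0 gives the rule: "The therapy will be considered safe in the absence of any grade 3 or greater AE considered related to RST-001". The protocol synopsis has the same rule and adds a time point: "The primary endpoint is safety at 6 months from start of study treatment". The SAP sentence carries no time window. Neither place gives a minimum denominator, a rate to be ruled out or an interval.

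On size, protocol 11.3.1 says that "no formal sample size computations to meet power requirements were made", and SAP 13.0 agrees. Phase 1 has three dose groups, "each group comprising of approximately but no less than three patients" (SAP 4.0). Phase 2a is optional: "In Phase 2a, up to 12 patients may be enrolled and receive RST-001 at the maximum tolerated dose" (SAP 4.0). Its size depends on whether the DSMC sees a treatment benefit in Phase 1. If it does, "then approximately 6 patients will be enrolled in Phase 2a and follow the same eligibility criteria as Phase 1" (protocol 3.15.1.2); if it does not, the number is about 12. The stated ceiling is "Up to approximately 21 patients will be enrolled in this study".

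On precision, SAP 11.1 tabulates adverse events as numbers and percentages, and SAP 15.1 does the same for categorical data in general. The one sentence on intervals is in SAP 10.0, under efficacy: "All confidence intervals will be 2-sided 95% confidence intervals, unless stated otherwise". It is attached to no safety output.

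On grading, protocol 8.1.3 records severity as mild, moderate or severe. CTCAE grade appears only in the synopsis and the stopping rules of protocol 7.4.

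**The concern.** Zero events in a small sample is weak evidence of a low event rate, yet the rule turns it into a yes/no conclusion on the primary objective. A reader of the final report would see the label without the uncertainty behind it.

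The number of patients behind the label is also not fixed. It depends on whether the sponsor opens Phase 2a and on the DSMC's view of efficacy. At any true rate above zero, a zero count is more likely with fewer patients, so a judgement about benefit changes how hard the safety criterion is to meet.

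The dose carried forward is the one that matters most, and fewer patients receive it than the total suggests.

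**Working it through.** **Plan's own figure.** Three groups of 3 plus 12 in Phase 2a gives 3×3 + 12 = 21, matching the stated ceiling. With 6 in Phase 2a the total is 3×3 + 6 = 15, and with no Phase 2a it is 9. There is no power or precision figure to reproduce.

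**Patients at the maximum tolerated dose.** One Phase 1 group plus Phase 2a gives 3 + 6 = 9 or 3 + 12 = 15.

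**Formulas.**
- Upper limit of the exact two-sided 95% interval with 0 events in n: 1 − 0.025^(1/n).
- Chance of meeting the rule at true rate p: (1 − p)^n, taking patients as independent with a common rate.

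The documents give no true rate; protocol 3.11.1.2 says the risks are unknown. The values of p below are assumptions.

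| n | What it represents | Upper limit, 0 events | p = 5% | p = 10% | p = 20% |
|---|---|---|---|---|---|
| 9 | Phase 1 only (pooled), or maximum tolerated dose with Phase 2a of 6 | 33.6% | 63.0% | 38.7% | 13.4% |
| 15 | Total with Phase 2a of 6 (pooled), or maximum tolerated dose with Phase 2a of 12 | 21.8% | 46.3% | 20.6% | 3.5% |
| 21 | Maximum total (pooled) | 16.1% | 34.1% | 10.9% | 0.9% |

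The last three columns give the chance of the safe verdict. For example, at n = 15 the limit is 1 − 0.025^(1/15) = 1 − 0.782 = 0.218, and at p = 10% the chance is 0.9^15 = 0.206. For a single Phase 1 group of 3, the limit is 1 − 0.025^(1/3) = 70.8%.

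**Size needed.** The smallest n for which zero events puts the two-sided limit below p is ln(0.025)/ln(1 − p), rounded up. That is 36 patients for 10% and 72 for 5%, both above the ceiling of 21.

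**Pooling.** The 15 and 21 totals combine three doses, so their limits assume one rate across doses. The dog study does not encourage that assumption: at Week 5, anterior uveitis findings were seen in 1/8, 3/8 and 8/8 eyes at low, mid and high dose (protocol 3.6.2.1). Those findings are not CTCAE grades and are used here only to show a dose trend.

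**The case against.** The strongest reply is that this is a first-in-human dose-escalation study and is openly descriptive. Its size was chosen empirically, cohorts of three are described as typical, and nobody claims power. Other ocular measures are summarised under the primary objective (protocol 11.1, SAP 11.2). The safe label appears in the synopsis and SAP 5.0, but not in protocol 11.1 or in SAP 11.1 and 11.2. Counts and percentages are planned for adverse events, so a reader could derive a bound from them. The table shells are in a separate document and might contain an interval.

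Much of this is fair. The missing power calculation is not the defect, and a reader should not infer that it is. Nor can one say that no interval will appear anywhere; one can say only that the protocol and SAP text attach none to a safety output. But the other ocular measures are not part of the criterion, and an interval in a shell would not change a rule that declares safety without reference to it.

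Three stronger readings are tempting but not supported:
- That the limits are rates of serious events. Protocol 8.1.2 defines seriousness separately; the rule concerns related Grade 3+ events.
- That the overall verdict could rest on three patients. A completed Phase 1 has at least 9, so n = 3 is only a per-dose figure. Enrolment cut short by a related Grade 3+ event cannot yield the label either, because that event fails the rule.
- That greater leniency with fewer patients is peculiar to this plan. Every zero-event criterion behaves this way. It matters here because n is left open.

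**Conclusion.** The concern holds. Applied as written, the rule gives a categorical conclusion that the design cannot support. With zero events, the related Grade 3+ rate at the maximum tolerated dose could still be as high as 33.6% (n = 9) or 21.8% (n = 15). Even the full pooled 21 leaves 16.1% not excluded, and only if one rate applies to all doses. At an assumed true rate of 10%, the label would be reached with probability 39%, 21% or 11% for n = 9, 15 and 21. The rule does screen out high rates at the larger sizes: at 20% and n = 21 it is met with probability 0.9%.

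The limits rest on groups of exactly three in Phase 1 (slightly larger groups would lower them a little), complete follow-up to Month 6 and independent patients.

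A separate difficulty is that the numerator is not clearly countable. The rule uses CTCAE grade, while adverse events are recorded and tabulated, and missing severities imputed (SAP 15.6), on a three-level scale. A reader might equate severe with Grade 3 or higher, but nothing in the documents says so.

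**What to change.** - In the synopsis and SAP 5.0, replace the safe label with the number and proportion of dosed patients who have a related CTCAE Grade 3+ adverse event by Month 6, with an exact (Clopper-Pearson) two-sided 95% interval. Stating the Month 6 window also closes the gap in the SAP sentence.
- Report this per dose. Make the maximum tolerated dose (its Phase 1 group plus Phase 2a) the main figure and the pooled figure supportive.
- In protocol 11.3.1 and SAP 13.0, state the upper limits for zero events at the maximum tolerated dose: 33.6% for n = 9 and 21.8% for n = 15. Give the pooled limits (21.8% for n = 15, 16.1% for n = 21) only with the note that they assume a common rate across doses.
- Reconcile the severity scale of protocol 8.1.3 with the CTCAE grade in the rule, so that the numerator can be counted.

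The reporting change costs new wording and a small amount of output, and the stated conclusion becomes less favourable. The grading step may cost more if CTCAE grade is not already collected for each event. Dosing, enrolment and stopping rules are not affected. The SAP still refers to protocol Amendment 2 while the protocol is at Amendment 4, so it needs revision anyway, and protocol 11.3.6 allows the analysis plan to be finalised up to database lock.
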